9.2.3 OTHER OUTCOME MEASURES

Other outcomes include:

- Tolerability of and adherence to oral medication
- Self-reported (by the parent/carer) symptoms in the child at each follow-up visit

Antimicrobial resistance outcomes are:

- Changes in nasopharyngeal carriage of antibiotic-resistant (e.g. penicillin non-susceptible, methicillin-resistant) Gram positive bacteria; assessed in a subset of children
- Changes in faecal carriage of extended spectrum beta-lactamases (ESBL)-producing Gram negative bacteria; assessed in a subset of children

Costs and cost-effectiveness will also be evaluated (see [Section 0](#)), as will pharmacokinetics of amoxicillin and co-amoxiclav (see [Section 10.1](#)).

9.2.4 PROTECTION FROM BIAS

It is not practical to use placebos for the multi-drug multi-duration regimens used in this trial, given the relatively large differences in numbers of tablets across the different weight-bands. Further the co-amoxiclav and amoxicillin tablets are different meaning a “double dummy” approach would be needed (each child receives either active co-amoxiclav and placebo amoxicillin or placebo co-amoxiclav and active amoxicillin). Introduction of placebo would therefore increase the pill burden substantially and will be logistically infeasible. It is also not ethical to give children sham IV treatment, which would also defeat one of the key purposes of the trial which is to investigate oral step-down as a mechanism to reduce length of hospitalisation.

Therefore, to counter the possibility of bias, objective outcome measures have been chosen as much as possible. The primary endpoint is re-admission to hospital or death within 28 days post-randomisation. Hospital admissions are clinically significant events and it is reasonable to assume, therefore, that they will be approximately ascertained without bias. The trial will pay for visits to the hospital, if required, within the follow-up period (where healthcare is not free of charge), meaning that parents/carers will have a reason to come back to the original hospital rather than go elsewhere. Every effort will be made to minimize losses to follow-up and to ascertain outcomes completely, thus avoiding bias from differential ascertainment between the randomised groups. Any child lost-to-follow-up will be traced for vital status based on location and mobile phone data verified before discharge (with consent for this). To further protect from bias, an independent Endpoint Review Committee will adjudicate on the causes of death and of hospitalisation (to enable an unbiased assessment of the secondary outcome, CAP-related readmission/death) and whether (without knowledge of actual randomisation) events were unlikely, possibly/probably or uncertainly to have been related to each intervention, were those affected to have received them. This will increase the objectivity of these assessments and increase consistency between sites.

Following recommendations in adults [52], we have avoided using a “test of cure” approach to define endpoints precisely because of substantial challenges in its unbiased assessment outside a placebo-controlled trial. In paediatric CAP, particularly in very young children, symptom recovery scores are also highly subjective and therefore we have not considered these as primary or secondary endpoints either.

Secondary outcomes include length of stay; hospitalisations will be paid for by the trial (if not free of charge) so there will be no pressure to discharge children differentially between randomised groups. Other secondary outcomes include change in antibiotics: the trial protocol (**Table 8**) and manual of operations will contain criteria supporting failure of antibiotic therapy and need to switch, promoting consistency in antibiotic management regardless of original randomisation and minimizing bias. The trial is, however, designed to be pragmatic and reflect what would happen in the real-world where, for example, WHO guidelines were to recommend stepping down to oral therapy for 4 days total duration; in that some children would still need to switch antibiotics and others continue beyond 4 days. What the trial will provide is estimates of these proportions and overall effects on outcomes.

9.3 SAMPLE SIZE

9.3.1 MAIN TRIAL (PEDI CAP-A)

1,000 children randomised 1:1 to oral step-down with amoxicillin vs co-amoxiclav provides >80% power to detect a 6% absolute reduction (corresponding to a 40% relative reduction) in 28-day re-admission or mortality (all-cause) from 15% (amoxicillin) to 9% (co-amoxiclav) assuming 5% lost-to-follow-up at 28-days post-randomisation (two-sided $\alpha=0.05$).

Randomizing 500 children between 5 equidistant duration groups for amoxicillin and for co-amoxiclav is sufficient to estimate the duration response curve within a 5% error margin in >95% of simulations [33].

For comparison of the co-amoxiclav step-down with the 5-day intravenous groups, randomising 500 vs 100 children respectively provides 89% power to demonstrate non-inferiority based on a 10% non-inferiority margin for a 9% failure rate (two-sided $\alpha=0.05$) (power is >80% for failure rates up to 12%). A 10% non-inferiority margin has been recommended by the United States (US) Food and Drug Administration (FDA) for adult bacterial CAP based on similar hypothesised event rates with and without antibiotics to those observed in children [53].

Therefore the total sample size for the main trial (PediCAP-A) is 1,100 (including the additional 5-day intravenous group). There is no formal adjustment for non-compliance because the trial is pragmatic, designed to evaluate the impact of strategic approaches to antibiotic choice and duration. Rather, non-compliance is a separate secondary outcome (incorporating change from allocated antibiotic regimen for any reason) which will be analysed separately, and the results of the primary analysis interpreted conditional on this.

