Interventions to be Compared	
All children will initiate or have already initiated treatment with WHO-recommended intravenous antibiotics.
 
In the main trial (PediCAP-A), children who have received at most 24h of intravenous antibiotics will be randomised to step-down from intravenous antibiotics when they are clinically stable and able to take oral medication to:
 
 ▪ either oral amoxicillin or oral co-amoxiclav (7:1 amoxicillin:clavulanate) (1:1), both as dispersible tablets ▪ for a total duration of 4, 5, 6, 7 or 8 days antibiotics (1:1:1:1) (from start of intravenous antibiotics); (total 10 groups) ▪ or to remain on intravenous antibiotics for a total of 5 days following current WHO recommendation (additional eleventh group of the same size as each duration/drug group). 
In the parallel Phase II PK trial (PediCAP-B), children who have received at most 24h of intravenous antibiotics will be randomised to step-down from intravenous antibiotics when they are clinically stable and able to take oral medication to

SUMMARY INFORMATION TYPE	SUMMARY DETAILS
	
 ▪ either oral co-amoxiclav 4:1 or 14:1 (1:1) for a total duration of 6 days antibiotics (from start of intravenous antibiotics) (two groups) 
All children will receive at least 24h of intravenous antibiotics before stepping down to oral medication.

Study Hypothesis	
PediCAP-A
 
 ▪ Oral co-amoxiclav step-down is superior to oral amoxicillin step-down for preventing readmission or death within 28 days of commencing treatment. ▪ Randomising children between 5 different total durations of antibiotics including intravenous plus oral step-down will identify the minimum duration providing outcome rates within specific thresholds of the WHO-recommended 5 days' intravenous regimen. 
PediCAP-A plus PediCAP-B
 
 ▪ Clavulanate PK exposures will be linear across the three formulation strengths used worldwide (4:1, 7:1, 14:1)
Primary Outcome Measure(s)	
For the main trial (PediCAP-A):
 
 ▪ Hospital readmission or death within 28 days of randomisation (all-cause) 
For the Phase II PK trial (PediCAP-B):
 
 ▪ Plasma exposure to amoxicillin and clavulanate

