1.4.3 RATIONALE FOR INCLUSION OF “BENCHMARKING” CONTINUOUS INTRAVENOUS GROUP

The challenge with antibiotic trials is identifying an appropriate “standard of care”, since current practice is often very variable in terms of both drug and duration, reflecting local opinion as well as local resistance patterns. However, were the trial to only include the durations above, even if we estimate the “duration-response” curve for each of amoxicillin and co-amoxiclav oral step-down, it would be reasonable to ask how these curves related to continuing on intravenous antibiotics for the whole duration of treatment, particularly since WHO guidance currently has variable recommendations for the duration of injectable antibiotics for severe pneumonia ranging from at least 5 to at least 10 days.

We will therefore add an 11th randomised group which will receive **5-day intravenous antibiotics with no oral step-down**. Hospitals participating in PediCAP who undertook a short epidemiological survey identified that more than 50% of children started on intravenous antibiotics for CAP stayed in hospital for at least 4 days or longer (see **Section 1.4.4**). The choice of five days is also in accordance with the minimal WHO recommendation, although clinical practice varies. As standard-of-care is variable, this is not a formal control group, but will enable the trial to “benchmark” the duration-response curve for each oral step-down option.

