9.5 ANALYSIS PLAN (BRIEF)

The analyses will be described in detail in a full Statistical Analysis Plan. This section briefly summarises the main issues.

The primary analysis population is intention-to-treat, including all randomised children, regardless of treatment received. This corresponds to estimating the impact of the effectiveness of the strategies of stepping down to oral amoxicillin vs co-amoxiclav and varying total duration of antibiotics. However, in secondary analyses we will also use inverse-probability weighting methods to adjust for deviation from randomised strategy, both duration of antibiotic treatment and oral-stepdown, which is a more efficient approach than defining a per-protocol population [55].

As follow-up is short (28 days post-randomisation) lost-to-follow-up should be low, and in each population, the primary comparison between randomised groups will be conducted using binomial regression, reported on the risk difference scale (following the sample size calculation which is based on risk differences). The primary analysis will adjust for the randomisation stratification factors (site and the other factorial randomisation). The primary analysis will be conducted on observed data. Secondary analyses will use multiple imputation with chained estimating equations to impute outcomes for the small (5%) number of expected missing outcomes due to losses to follow-up before 28 days post-randomisation (the sample size calculation in [Section 9.3](#) includes an inflation factor to allow for this). Imputation will be done separately within each randomised group to allow for unknown interactions, and will be based on outcomes and main baseline characteristics as recommended. Duration-response curves will be estimated separately for oral amoxicillin and oral co-amoxiclav randomised groups using fractional polynomials to flexibly model the impact of duration on response following Quartagno et al [33]. A combined model will test whether there is evidence that these duration-response curves vary between co-amoxiclav and amoxicillin using main effects and interactions (i.e. subgroup effects), specifically the following key factors:

- site

- severity
- age
- HIV infection and exposure
- malnutrition (assessed by weight-for-height Z-scores, according to the WHO Growth Standards, and pedal oedema/MUAC)

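### The 89% power for co-amoxiclav versus 5-day IV belongs to a contrast pooled over 4 to 8 days, which cannot support a non-inferiority claim for any single duration, and it leaves out the 5% loss to follow-up

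*Protocol*

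**What the plan says.** Section 9.3.1 gives the IV group a formal test: "randomising 500 vs 100 children respectively provides 89% power to demonstrate non-inferiority based on a 10% non-inferiority margin for a 9% failure rate", at two-sided alpha 0.05, with power said to stay above 80% for failure rates up to 12%. The 500 are all children randomised to co-amoxiclav 7:1, about 100 at each of 4, 5, 6, 7 and 8 days. The 100 are the eleventh group, on IV for 5 days.

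Three other places bear on this test.

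- The study hypothesis in the Summary of Trial says that randomising between durations "will identify the minimum duration providing outcome rates within specific thresholds of the WHO-recommended 5 days' intravenous regimen". That is a statement about individual durations compared with IV.
- Section 1.4.3 says of the IV group that "this is not a formal control group", and gives its role as benchmarking the duration-response curve of each oral option.
- On loss to follow-up, section 9.3.1 writes "assuming 5% lost-to-follow-up at 28-days post-randomisation" for the amoxicillin versus co-amoxiclav comparison and does not repeat it for the IV comparison. Sections 6.9 and 9.5 say, without limiting it to one comparison, that the sample size calculation includes an inflation factor for loss.

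**The concern.** This is the only comparison with the WHO-recommended IV regimen for which the protocol gives a margin and a power. It averages over five durations, whereas the hypothesis and the likely use of the result concern one duration at a time. Section 9.2.4 itself uses a guideline recommending 4 days in total as its example of application. A finding that step-down is non-inferior to IV could then be read as covering 4 days, when the longer courses might have carried the average.

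The stated power also appears to rest on every randomised child having an outcome, which is not what sections 6.9 and 9.5 describe.

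**Working it through.** **Inputs.** Margin 10 points, 9% (or 12%) failure in both groups, two-sided alpha 0.05, 500 v 100, and 5% loss, all from section 9.3.1. There are 100 children per randomised group (Summary of Trial).

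**Formula.** Unpooled normal approximation: power = Φ(0.10/SE − 1.96), with SE = √[p(1−p)(1/n_oral + 1/n_IV)].

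**1. Reproducing the stated figures, no loss.**
- 9%, 500 v 100: SE = √[0.0819 × (1/500 + 1/100)] = 0.03135; 0.10/0.03135 = 3.190; Φ(1.230) = 89.1%.
- 12%, 500 v 100: SE = 0.03560; Φ(0.849) = 80.2%.

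Both agree with the protocol, so this is very probably the method used.

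**2. The same formula with 5% loss, 475 v 95.**
- 9%: SE = 0.03216; Φ(1.149) = 87.5%.
- 12%: SE = 0.03652; Φ(0.778) = 78.2%.

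Under this formula, 80% power with loss is reached only up to about 11.4% failure.

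**3. Dependence on method.** Exact power of a test based on the Wald interval, 475 v 95, is 93.7% at 9% and 83.3% at 12%. The shortfall at 12% therefore belongs to the approximation that reproduces the 89%. Section 9.3.1 does not name its method.

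**4. What the pooled contrast can miss (assumed rates).** Let IV be 9%, co-amoxiclav at 4 days 19% (exactly at the margin), and co-amoxiclav at 5 to 8 days 9%.
- Pooled co-amoxiclav risk = (19 + 4 × 9)/5 = 11%, so the true pooled difference is 2 points.
- SE = √(0.09 × 0.91/95 + 0.11 × 0.89/475) = 0.0327.
- Probability of declaring non-inferiority = Φ((0.10 − 0.02)/0.0327 − 1.96) = Φ(0.49) ≈ 69%. The exact Wald calculation gives 73%.

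In a milder case, mean oral duration is 6 days against 5 for IV. If failure fell linearly by an assumed 0.5 to 2 points per day, the pooled difference would shift by 0.5 to 2 points in favour of co-amoxiclav.

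**5. Power of a 5-day v 5-day contrast** (9% failure):

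| Estimate of co-amoxiclav risk at 5 days | Effective oral n, no loss / 5% loss | Power, no loss / 5% loss |
|---|---|---|
| 5-day group alone | 100 / 95 | 69.5% / 67.3% |
| Quadratic curve, all co-amoxiclav | 269 / 256 | 84.7% / 82.9% |
| Linear curve, all co-amoxiclav | 333 / 317 | 86.5% / 84.8% |
| Pooled over durations (not a 5-day risk) | 500 / 475 | 89.1% / 87.5% |

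For the linear row, the five durations have variance 2 and day 5 lies one day from the mean, so the variance factor is (1 + 1/2)/475 and the effective n is 475/1.5 = 317. The quadratic row comes from the corresponding design matrix.

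**The case against.** The strongest defence is that nothing in the power statement is miscalculated. Both figures reproduce, writing 500 v 100 makes the pooling visible, and intention-to-treat comparison of a step-down strategy with 5-day IV is a legitimate randomised contrast that needs no model. Duration is a separate co-primary objective (section 1.5), answered by curves fitted for each oral drug (section 9.5), and a failing 4-day group is also covered by the stopping guideline for the minimum duration (section 9.4). The scenario in step 4 assumes a cliff at 4 days and a reader who ignores those curves. All of this stands. It limits the point to what may be concluded from the pooled test, and it is a reason to keep that test.

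A reader might go further and infer that section 9.5 itself cuts the comparison to 100 v 100, because it says "The primary analysis will adjust for the randomisation stratification factors (site and the other factorial randomisation" and duration is the other randomisation. The text does not support that. The IV group lies outside the factorial, so the clause cannot be carried over to it. Even if duration were adjusted for, the 67% to 70% follows only if duration enters as separate categories and the amoxicillin groups lend no information. Adding those groups in an additive model gives 78.9%, or 76.8% with loss. The smooth curves in step 5 give 83% to 87%, and section 9.5 already plans to model duration smoothly.

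On section 1.4.3, one can say that sizing a benchmark group with a margin does not make it a formal control. That is arguable, but a reader is still left unsure whether the test in section 9.3.1 is confirmatory.

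**Conclusion.** The point holds in a limited form. The 89% is correct arithmetic for co-amoxiclav pooled over 4 to 8 days against 5-day IV with complete follow-up. That contrast does not address the hypothesis about individual durations relative to IV, and on its own cannot support a non-inferiority statement about any one of them. The 69% to 73% rests on the assumed failure rates in step 4 and illustrates the risk; it does not predict results.

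With the protocol's own 5% loss, the approximation that reproduces the stated power gives 87.5% at 9% failure and 78.2% at 12%. The statement of more than 80% up to 12% is then not met by that method, although exact Wald power (83.3%) would meet it. The size of this is small, and stating the method and the loss settles it.

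It should not be concluded that the protocol's analysis reduces power to 67% to 70%, or that the pooled comparison is invalid. Whether a duration-specific difference should replace the pooled one as the main contrast is a matter of preference.

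**What to change.** - **Sections 9.3.1 and 9.5:** label the 500 v 100 contrast as pooled over durations. Restate its power at 475 v 95 (87.5% at 9%, 78.2% at 12% by the normal approximation) and name the method; if an exact Wald calculation is preferred, give 93.7% and 83.3%.
- **Section 9.5:** alongside the pooled result, report the co-amoxiclav minus IV risk difference with its confidence interval at each of 4, 5, 6, 7 and 8 days, from the duration-response model already planned. Base any non-inferiority statement about a particular duration on these, and not on the pooled test.
- **Section 9.3.1:** state the power of the 5-day contrast with loss, about 83% to 85% under a quadratic or linear curve and 67% from the 5-day groups alone.
- **Sections 1.4.3 and 9.3.1:** use one description of the IV group's role, so that it is clear whether the non-inferiority test is formal or a benchmark.

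The cost is wording in the protocol and the matching entry in the SAP, a slightly less favourable power statement if the normal approximation is kept, and duration-specific estimates that depend on the fitted curve. No extra children or data are needed.

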5.2 INTRAVENOUS ANTIBIOTICS (ALL CHILDREN)

5.2.1 PRODUCTS & TREATMENT SCHEDULE

At the point of randomisation, children should have received no more than 24h of intravenous antibiotics ([Section 3](#)). However, standard-of-care intravenous treatment should be for at least 24 hours for all children, whether randomised to oral step-down or continuous intravenous antibiotics and regardless of what duration of intravenous antibiotics has been received at the point of randomisation. That is, children randomised to step-down to oral antibiotics should not do so before receiving at least 24h of intravenous antibiotics. Those randomised to intravenous antibiotics will be treated with intravenous antibiotics for 5 days in total (from start of intravenous antibiotics, excluding oral/intramuscular antibiotics received in the community). Parents/carers of children randomised to 5 days' IV will receive travel costs for any additional days their child remains in

hospital solely for the purpose of receiving intravenous antibiotics within the trial, since a few of these children might otherwise be discharged early on oral antibiotics depending on local practice (site-specific).

Dosing should follow the local standards of care (summarised in [Table 6](#)) which generally follow WHO recommendations where given ([Table 2](#)). Local standards of care may differ from WHO recommendations due to factors such as local susceptibility patterns, drug availability and institutional prescribing guidelines.

The choice of intravenous antibiotics will be made by the treating physician prior to randomisation. Doses should be given intravenously: if there is a problem with venous access, then isolated post-randomisation doses that should have been given intravenously may be given intramuscularly. Doses will be dispensed from ward stock and prepared and given by the ward nurses. Children will be hospitalised for the entire parenterally administered treatment duration (5 days for those randomised to intravenous antibiotics). After completing their intravenous antibiotics (either after 5 days or after moving to oral-stepdown), children should be discharged as soon as they are clinically stable.

Table 6: Dosing of standard intravenous antibiotics

DRUG	SCHEDULE
Ampicillin	IV/IM: 50 mg/kg every 6 hours
Benzylpenicillin (penicillin G)	IV: 50'000-100'000 U/kg every 6 hours
Cefotaxime	IV: 50 mg/kg every 6 hours or 33.3 mg/kg every 8 hours

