9.4 INTERIM MONITORING & ANALYSES

A Data Monitoring Committee (DMC) Charter will be drawn up that describes the membership of the DMC, relationships with other committees, terms of reference, decision-making processes, and the timing and frequency of interim analyses. The Charter will also contain a description of stopping guidelines: at minimum, these will contain a recommendation for early stopping of the minimum duration group if there is evidence beyond reasonable doubt (Haybittle-Peto stopping rule) that the minimum duration is inferior to the maximum duration on the primary endpoint, with a similar stopping guideline for the comparison of the two oral formulations.

The DMC will meet within 6 months after the trial opens; although the DMC will in general meet annually, the frequency of subsequent meetings will be determined by the DMC and could be more frequent if deemed necessary. The DMC can recommend premature closure or reporting of the trial, or that recruitment to any randomised group be discontinued or modified. Such recommendations would be made if, in the view of the DMC, there is proof beyond reasonable doubt that one of the allocated strategies is better than its comparator in terms of a difference of clinically significant magnitude in a primary outcome.

The guiding statistical criteria for “proof beyond reasonable doubt” is a Haybittle-Peto type rule based on the 99.9% confidence interval in each interim analysis for both superiority and non-inferiority comparisons [54]. See [Section 0](#) for details on DMC membership.

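### The 5-day IV group is described as a benchmark, not a formal control, yet section 9.3.1 powers a non-inferiority claim against it with a 10-point margin that its stated rationale does not support

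*Protocol*

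**What the plan says.** Protocol section 1.4.3 explains why an eleventh group on 5 days of intravenous antibiotics was added. It states: "As standard-of-care is variable, this is not a formal control group". The group's role there is to give a reference for the duration-response curves.

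Section 9.3.1 then sizes a comparison with that group. It opens "For comparison of the co-amoxiclav step-down with the 5-day intravenous groups" and says that 500 v 100 children "provides 89% power to demonstrate non-inferiority based on a 10% non-inferiority margin for a 9% failure rate" at two-sided alpha 0.05, with power above 80% for failure rates up to 12%. The margin is supported by a regulatory recommendation for adult bacterial pneumonia, described as "based on similar hypothesised event rates with and without antibiotics to those observed in children".

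The same section says of the two oral drugs, on the same endpoint, that the sample "provides >80% power to detect a 6% absolute reduction (corresponding to a 40% relative reduction"), from 15% to 9%, assuming 5% loss to follow-up.

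Section 5.2.1 requires that "children randomised to step-down to oral antibiotics should not do so before receiving at least 24h of intravenous antibiotics".

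Two other places bear on the point. The second PediCAP-A hypothesis in the trial summary looks for the shortest duration whose outcome rates fall within thresholds of the 5-day intravenous regimen; it does not state the thresholds. Section 9.4 describes a Haybittle-Peto type guideline "based on the 99.9% confidence interval in each interim analysis for both superiority and non-inferiority comparisons". The brief analysis plan in 9.5 sets out no non-inferiority analysis against the intravenous group.

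**The concern.** The first problem is one of status. If the intravenous group is only a benchmark, a powered demonstration of non-inferiority against it is out of place. If that demonstration is intended, the group is in effect a control and section 1.4.3 is wrong.

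The second problem is the margin.

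- It is larger than the assumed event rate, for an endpoint that includes death.
- It is larger than the difference the trial is built to detect between two oral drugs on that endpoint. A deficit of that size against the WHO-recommended regimen would lie inside the acceptable zone.
- Its rationale concerns antibiotics against none. In this trial the groups share the initial intravenous treatment and both then continue antibiotics. They differ only in route, drug and length of the later part. A margin drawn from the whole antibiotic effect does not by itself protect the contribution of that later part.

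The results are meant to inform treatment guidelines. A statement that co-amoxiclav step-down is non-inferior to 5 days of intravenous treatment would carry more weight than this margin earns.

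**Working it through.** **Inputs (all from 9.3.1).** Co-amoxiclav n = 500, intravenous n = 100; failure rate 9% in both (alternative 12%); margin 10 points; two-sided alpha 0.05; 5% loss, stated for the drug comparison; drug-comparison rates 15% and 9%.

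**Formula.** Power = Φ((margin − true difference)/SE − 1.96), with SE = √(p₁(1−p₁)/n₁ + p₂(1−p₂)/n₂).

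**1. Reproducing the stated power.**
- 9% in both: SE = √(0.09 × 0.91 × (1/500 + 1/100)) = 3.135 points; Φ(10/3.135 − 1.96) = 89.1%. This matches the stated 89%.
- 12% in both: SE = √(0.12 × 0.88 × (1/500 + 1/100)) = 3.560 points; Φ(10/3.560 − 1.96) = 80.2%. This matches the claim of more than 80%.

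Both figures use full numbers, with no loss to follow-up.

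**2. With the 5% loss (475 v 95).**
- 9%: SE = 3.216; power 87.5%.
- 12%: SE = 3.652; power 78.2%, below 80%.

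**3. What the margin tolerates.** 9% + 10 points = 19%, a relative risk of 19/9 = 2.1.

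**4. Chance of declaring non-inferiority at 500 v 100 when co-amoxiclav is truly worse (intravenous 9%).**
- True 15%: SE = √(0.15 × 0.85/500 + 0.09 × 0.91/100) = 3.277; Φ((10 − 6)/3.277 − 1.96) = 23.0%. Exact enumeration over all possible results gives 19.2% with a Wald interval and 30.6% with a Newcombe interval.
- True 18%: SE = 3.338; Φ((10 − 9)/3.338 − 1.96) = 4.8%. Exact enumeration gives 3.1% (Wald) and 6.2% (Newcombe).

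**5. What observed results would pass, with 9/100 intravenous events.**
- Highest passing co-amoxiclav count: 63/500 (12.6%) by Wald, 68/500 (13.6%) by Newcombe.
- Observed 15% v 9%: upper limit 12.4 points (Wald) or 11.4 (Newcombe); fails.
- Observed 18% v 9%: difference 9 points, 95% CI 9 ± 1.96 × 3.338 = +2.5 to +15.5; fails.

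**6. Precision if the comparison is reported as an estimate.** At 9% in both groups the half-width is 1.96 × 3.135 = 6.1 points, or 1.96 × 3.216 = 6.3 points after loss.

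**The case against.** Several counter-arguments deserve weight.

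- **The margin has a stated source.** It is a regulatory recommendation, with event rates said to be similar in children. That source is not in the document, so one cannot say how much of the antibiotic effect 10 points would preserve. This stands: the margin is weakly supported for this contrast, not unsupported.
- **Six points is a planning effect, not a maximum acceptable loss.** The comparison with intravenous treatment has other trade-offs, such as earlier discharge and fewer line complications. This also stands. The 6-point figure shows an unexplained tension inside 9.3.1; it does not show that a margin must be 6 or less.
- **A benchmark can still be compared with some power.** Section 1.4.3 denies formal control status because standard of care varies, and 9.5 gives no decision rule. Detail may sit in the analysis plan, which is not shown. That leaves the operative test open, but 9.3.1 still speaks of demonstrating non-inferiority at a stated margin and alpha.
- **The trial summary does contain a threshold hypothesis against the intravenous regimen.** A comparison with that group is therefore not foreign to the trial. The hypothesis concerns durations, however, and gives no thresholds; 9.3.1 concerns pooled co-amoxiclav.

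A reader might infer that the plan would readily pass a strategy that doubles readmission or death, because a true 18% lies inside the margin. The calculation does not support that: such a strategy passes in about 3-6% of trials, and an observed doubling at the planned rate fails. A reader might also infer that 9.4 sets a stopping rule for this comparison. It never names the intravenous group; only its general reference to non-inferiority comparisons could reach it.

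**Conclusion.** The concern holds as an inconsistency about the group's status and as a margin that does not fit the contrast. The 89% is not an arithmetic error.

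Its practical size is the 19-31% chance, depending on the interval method, of declaring co-amoxiclav step-down non-inferior when it is truly worse by 6 points (15% v 9%). This assumes 500 v 100 children and a 10-point criterion applied to a two-sided 95% interval.

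A secondary point is that the power statement omits the 5% loss used earlier in the same section. By the formula that reproduces the protocol's own figures, power falls to 87.5% at 9% and 78% at 12%, so the claim of more than 80% up to 12% no longer holds on that basis.

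Neither co-primary objective in section 1.5 is framed as this non-inferiority comparison. The consequence is confined to what may be claimed about co-amoxiclav step-down against 5 days of intravenous treatment.

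**What to change.** Reconcile section 1.4.3, the duration hypothesis in the trial summary and section 9.3.1, so that they give the intravenous group one role.

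In 9.3.1, replace the 10-point non-inferiority claim for pooled co-amoxiclav v 5-day intravenous treatment with a benchmark risk difference and its 95% confidence interval. State the expected precision: about ±6 points at a 9% rate.

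If the sponsor prefers to keep a margin, it should justify that margin for the part of the course that differs between the groups and against the 9% event rate. It should also restate power with the 5% loss (87.5% at 9%, 78% at 12%) and drop or amend the statement about rates up to 12%. No particular margin is proposed here.

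In 9.4, one sentence is enough: say whether the reference to non-inferiority comparisons includes the intravenous group.

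The cost is wording only. No extra children are needed, and the group's size is unaffected because the trial summary sets it equal to each drug-by-duration group. What is given up is a formal non-inferiority claim for a group already labelled a benchmark.
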